### 4.3. Secondary Endpoints Analyses

### 4.3.1. Definition of endpoints

The secondary endpoints are:

- Change from baseline in mean symptom score for rhinorrhoea (runny nose) VRS from Week 49 through to Week 52
- Change from baseline in mean symptom score for loss of smell VRS from Week 49 through to Week 52
- Change from baseline in Lund Mackay (LMK) CT score at Week 52
- Change from baseline in SNOT-22 total score at Week 52
- Change from baseline in mean nasal obstruction score VRS from Week 21 through to Week 24
- Change from baseline in total endoscopic NP score at Week 26

The VRS endpoints collected daily in the morning via the eDiary will be handled in the same way as the co-primary VRS endpoint, with daily data being collapsed into 4-week time periods as described in Section 6.3.4.2. A CDF plot will also be provided for the change from baseline by treatment group for the endpoints: (1) Change from baseline in mean symptom score for rhinorrhoea (runny nose) (VRS) from Week 49 through to Week 52 and (2) Change from baseline in mean symptom score for loss of smell (VRS) from Week 49 through to Week 52.

A computed tomography (CT) scan is performed at Visit 16 (Week 52) and all image recordings of CT scans will be sent to an independent reviewer for centralized blinded data assessment. The central reading for LMK scoring will be used for analysis. The LMK CT scoring system is based on localization with points given for degree of opacification: 0 = normal, 1 = partial opacification, 2 = total opacification. These points are applied to the maxillary, anterior ethmoid, posterior ethmoid, sphenoid, frontal sinus on each side. The osteomeatal complex (OC) is graded as 0 = not occluded, or 2 = occluded deriving a maximum score of 12 per side. The combined score will range from 0-24 with higher scores indicating greater disease severity. Non-missing scores must be available for all portions on both sides for the combined score to be calculated; otherwise the score will be set to a value of 9 to indicate a missing or unreadable value.

SNOT-22 is a 22-item questionnaire that will be completed at each of the scheduled clinic visits using the eDiary. Participants will be asked to rate the severity of their condition on each of the 22 items over the previous 2 weeks using a 6-point rating scale of 0-5 including: 0 = Not present/no problem; 1 = Very mild problem; 2 = Mild or slight

problem; 3 = Moderate problem; 4 = Severe problem; 5 = Problem as "bad as it can be". The total score range for the SNOT-22 is 0-110, where higher scores indicate greater disease impact. All questions must be answered to generate an overall score; if any individual questions are missing then the overall score will be missing.

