8.2.3. Computed Tomography (CT) Scan

CT scan is mandatory unless not approved by local ethics committee or institutional review board. The first CT scan must be performed prior to randomization and should be the last assessment performed, where possible. If the first CT scan cannot be performed as the last assessment before randomization, the subject should have completed their screening visit, and all screening lab results, the central NP score and ECG central over-read results should be assessed by the PI before a CT scan is conducted. The second CT scan should be performed at V16 or EW visit (up to 14 days prior to the nominal study visit). Note: If a participant is permanently discontinued both from the study intervention and from the study, and the second dose of study intervention was not received, decision on performing CT scan during Early Withdrawal visit at Week 26 will be made by the investigator in consultation with the Medical Monitor.

The Lund Mackay (LMK) CT scoring system is based on localization with points given for degree of opacification: 0 = normal, 1 = partial opacification, 2 = total opacification. These points are applied to the maxillary, anterior ethmoid, posterior ethmoid, sphenoid, frontal sinus on each side. The osteomeatal complex (OC) is graded as 0 = not occluded, or 2 = occluded deriving a maximum score of 12 per side. This scoring system has been validated in several studies.

All image recordings of CT scans will be sent to an independent reviewer at Clario for centralized blinded data assessment and central reading for LMK scoring will be used for analysis.

For participants in whom the OC is missing (because of a previous surgery) the reader should consider the location of the former OC and provide a scoring (as if the OC was there).

Detailed information on the CT assessment will be available in a separate operational manual provided to the sites. CT scans central reading for LMK scoring will be used in the statistical analysis.

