# 2.1. Multiplicity Adjustment

The hypotheses to be tested are structured as shown in Figure 1. The co-primary endpoints will be tested first and if these comparisons are both significant at the 2-sided 5% level, testing will continue for the secondary endpoints within the study according to the testing procedure detailed in Figure 1. Testing of secondary endpoints will be carried out in a hierarchical manner, dependent on statistical significance having been achieved for the previous endpoint in the hierarchy. Other pairwise comparisons will be performed

but are not part of the multiple testing strategy. Analyses of other efficacy measures are nested under the secondary efficacy measures and no multiplicity adjustment is planned for these other efficacy endpoints. The analyses for these other efficacy endpoints and some of the earlier time points for some of the co-primary and secondary endpoints are not adjusted for multiplicity and so nominal significance will be evaluated in a descriptive manner with these analyses using a 5% reference level.

A pre-specified pooled analysis of data from the ANCHOR-1 and ANCHOR-2 studies is planned for the secondary endpoints of time to first nasal surgery (actual or entry on waiting list) or disease-modulating medication for CRSwNP, time to first nasal surgery (actual) or disease-modulating medication for CRSwNP, proportion of participants requiring at least 1 course of systemic corticosteroids or disease-modulating medication for CRSwNP or nasal surgery (actual), and change from baseline in ACQ-5 score in participants with an ACQ score of >0.75 at baseline. This pooled analysis will be carried out after statistical significance is achieved for both co-primary endpoints within both studies. The closed-testing manner for the pre-specified pooled hierarchy is described further in the pooled SAP.

Figure 1 Conceptualization of Statistical Testing Strategy Across Studies ANCHOR-1 and ANCHOR-2

Note: Endpoint names in Figure 1 are abbreviated. Refer to Section 1.1 for full nomenclature of endpoints.

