#### 4.1.2. Baseline Definition

For all visit-based endpoints, including the co-primary endpoint of endoscopic NP score, baseline will be defined as the latest non-missing measurement collected prior to the first dose of study treatment. This will generally be from the Day 1 (Visit 2) assessment but may be from an unscheduled or screening assessment. In the case a visit-based assessment was collected after the first dose of study treatment, but still on the day of the randomization visit on Day 1 (Visit 2), then that assessment may be used.

For daily efficacy endpoints collected in the eDiary, baseline will be the average score from the 28 calendar days up to and including the date of randomization. This means the average will be based on the non-missing data from Day -27 to Day 1 inclusive. There must be a minimum of 4 non-missing values from Day -6 to Day 1 inclusive in order to derive the baseline, otherwise it will be set to missing.

Unless otherwise stated, if baseline data is missing no derivation will be performed and baseline will be set to missing.

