### **Model Specification**

 Statistical analyses for the change from baseline in Lund Mackay CT score at Week 52 will be performed using an analysis of covariance (ANCOVA) model with covariates of treatment group, baseline score, log(e) baseline blood eosinophil count, region and previous surgery for nasal polyps.

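### The SAP codes a missing or unreadable Lund-Mackay total as 9, which is a real score on the 0 to 24 scale, and gives no rule that keeps coded records out of the analysis

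*SAP*

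**What the plan says.** SAP 4.3.1 defines the Lund-Mackay total from five sinuses per side scored 0, 1 or 2 and an osteomeatal complex per side scored 0 or 2. It states the range: "The combined score will range from 0-24 with higher scores indicating greater disease severity". The next sentence deals with incomplete readings. Every portion has to be scored "on both sides for the combined score to be calculated; otherwise the score will be set to a value of 9 to indicate a missing" total, and an unreadable one is treated alike.

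The same code appears in SAP 4.2.1 for the endoscopic nasal polyp (NP) score, whose range is 0 to 8. SNOT-22, defined directly after Lund-Mackay in 4.3.1, has no numeric code: "if any individual questions are missing then the overall score will be missing".

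SAP 4.3.2 analyses the Week 52 change in Lund-Mackay with an "analysis of covariance (ANCOVA) model with covariates of treatment group, baseline score" and further terms, and asks for summary statistics for every secondary endpoint. Neither place mentions the code. Under SAP 4.1.2, for visit-based endpoints, "baseline will be defined as the latest non-missing measurement collected prior to the first dose of study treatment". Under SAP 2.1, "Testing of secondary endpoints will be carried out in a hierarchical manner"; the position of Lund-Mackay is in a figure that is not available here.

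**The concern.** A missing-value code has to lie outside the range of the variable. This one lies inside it. Once only the total is stored, an unreadable scan and a genuine total of 9 look the same. Keeping all 9s analyses unreadable scans as real and fairly low scores. Deleting all 9s removes participants with valid scans. Component scores or a flag would separate the two, but the SAP calls for neither.

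The rule names no visit. If it is applied to a pre-dose scan, a numeric 9 could also pass as the latest available value and enter the model as a baseline covariate.

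Lund-Mackay has one post-baseline value per participant, so no neighbouring visit dilutes a wrong one. For a single record the error can be large: with an assumed baseline of 18 and an unreadable Week 52 scan, the recorded change is 9 − 18 = −9, an apparent marked improvement. Some missing CT data are foreseen. Protocol 8.2.3 says "CT scan is mandatory unless not approved by local ethics committee or institutional review board", and leaves the scan at a Week 26 early-withdrawal visit to the investigator's decision in consultation with the Medical Monitor.

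**Working it through.** **1. The range, and whether 9 can occur.** Inputs are the scoring rules in SAP 4.3.1, which Protocol Appendix 9 confirms. The maximum per side is 5 × 2 + 2 = 12, so the maximum total is 24, as the SAP states. The number of component patterns giving each total is the matching coefficient of (1 + x + x²)^10 × (1 + x²)^2. All coefficients from 0 to 24 are positive, so every integer is attainable. The coefficient at 9 is 19,282, out of 3^10 × 2² = 236,196 patterns (8.2%). This is a share of patterns, not of patients. The NP score stops at 8, so 9 cannot occur there.

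**2. Search for a repairing rule.**
- SAP 4.3.2 (summaries, model, diagnostics, presentation): no conversion, flag or exclusion.
- SAP 4.1.2 (baseline) and 4.2.1 (missing at random): both speak of missing data and do not mention the code.
- Protocol 9.3.1: Lund-Mackay is handled like the co-primaries, with no mention of the code.

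**3. If coded records are analysed as 9.** With unreadable fraction f, an arm mean becomes (1 − f) × mean + 9f. The difference (active − placebo) therefore moves by

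f_placebo × (mean_placebo − 9) − f_active × (mean_active − 9).

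With equal f, this gives (1 − f) × the true difference whatever the means: a shrinkage of 2%, 5% or 10% for f = 2%, 5% or 10%. Examples with assumed Week 52 means (the documents give none):

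| Placebo / active mean | Unreadable, placebo / active | True difference | Difference obtained |
|---|---|---|---|
| 18 / 14 | 5% / 5% | −4.00 | −3.80 |
| 18 / 14 | 10% / 5% | −4.00 | −4 + 0.10 × 9 − 0.05 × 5 = −3.35 |
| 18 / 14 | 5% / 10% | −4.00 | −4 + 0.05 × 9 − 0.10 × 5 = −4.05 |
| 18 / 18 | 5% / 10% | 0 | 0.05 × 9 − 0.10 × 9 = −0.45 |

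**4. Effect on power.** ANCOVA simulation of change on treatment and baseline, 6,000 replicates. The 118 per arm comes from SAP section 5. Everything else is assumed: SD 5, baseline correlation 0.5, nominal difference −1.5, 5% unreadable in both arms, scores rounded and clipped to 0–24, significance at |t| > 1.97.

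| Week 52 mean, placebo / active (baseline) | Power, total set to missing | Power, analysed as 9 |
|---|---|---|
| 9.5 / 8 (13) | 71% | 71% |
| 13.5 / 12 (17) | 73% | 70% |
| 16.5 / 15 (18) | 72% | 65% |
| 19.5 / 18 (19) | 69% | 59% |

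The loss is 0 to 10 points. The ratio of standard errors (analysed as 9 over set to missing) runs from 0.96 to 1.09. A repeat run gave losses of about 1 to 12 points at 5% unreadable and about 0 to 5 at 2%.

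**5. If all 9s are deleted instead.** With q = P(score = 9), an arm mean becomes (mean − 9q)/(1 − q). Example with discretised normal scores, SD 5, nominal means 13.5 and 10 (13.47 and 10.04 after rounding and clipping):
- placebo, q = 5.32%: (13.473 − 0.479)/0.947 = 13.72;
- active, q = 7.81%: (10.038 − 0.703)/0.922 = 10.13.

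The difference goes from −3.44 to −3.60. Over placebo/active means of 9.5/8, 13.5/10, 16.5/13 and 19.5/15 with SD 4, 5 and 6, about 0.4% to 9.9% of an arm with valid scans is lost. The difference moves by about −0.16 to +0.17 points.

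**The case against.** The strongest reply is that the intent is plain. The rule says a 9 is there to mark a missing or unreadable value, so analysing it as a score contradicts the SAP's own sentence, and a baseline so labelled should not count as non-missing. Whoever derives the total must look at the components and can tell the cases apart. The SAP also leaves detail to a Programming Specifications document, which is not available here and may contain a conversion.

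The point about intent stands: this looks like wording that suits the NP scale and was used on a scale where it does not. It does not repair the code, because the SAP asks for a stored value that cannot be told from a real score and keeps nothing to separate them. A conversion may exist elsewhere; what can be said is that the SAP states none.

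Several limits on the size also stand:
- A scan never taken may generate no total at all. The clear exposure is incomplete or unreadable central readings, for which no rate is given.
- Participants with surgery or disease-modulating medication take the worst value, and Protocol 8.2.3 has a surgically absent osteomeatal complex scored.
- The simulation leaves out those worst-value assignments. Its 118 per arm is already net of the 5% non-evaluable allowance, so its 5% unreadable comes on top.
- The largest power loss needs the highest assumed means. At 1% unreadable, losses are about 0 to 2 points.

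**Conclusion.** The concern holds. The code 9 is a valid Lund-Mackay total, and nothing in the protocol or SAP removes coded records from the ANCOVA or the summaries. Entry into the analysis is a risk the text leaves open, not a step it prescribes. That 9 is attainable and that equal rates f shrink the difference by f follow from the scoring rule and simple algebra. The power losses (0 to 10 points at 5% unreadable) and the shift from deleting 9s (under 0.2 points either way) rest on assumed means, SDs, correlation and rates. The documents fix neither the direction nor the size of any bias. The co-primary results are not affected. It should be fixed because the endpoint is in the testing hierarchy and the remedy is trivial.

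**What to change.** In SAP 4.3.1, replace the 9 rule for Lund-Mackay with this: if any component is missing or unreadable, the total is set to missing, and readability is held in a separate flag; this applies to baseline and Week 52 scans. It then matches the SNOT-22 rule in the same section. The NP score code in SAP 4.2.1 can stay, with a statement that 9s are treated as missing in the analysis. The cost is one sentence in the SAP and one line in the derivation program. No sample size or power statement in the plan changes.

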### 4.3.2. Main analytical approach

Change from baseline in LMK CT score at Week 52 will be analyzed as described below. All other secondary endpoints will be analyzed in the same way as the co-primary endpoints. Summary statistics will be produced for each visit/4-week time-period by treatment group for each secondary endpoint. The same secondary endpoints analyses will be performed using the FAS-Modified analysis set as an additional analysis.

### **Model Specification**

 Statistical analyses for the change from baseline in Lund Mackay CT score at Week 52 will be performed using an analysis of covariance (ANCOVA) model with covariates of treatment group, baseline score, log(e) baseline blood eosinophil count, region and previous surgery for nasal polyps.

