	Change from baseline in mean rhinorrhoea (runny nose) score, mean loss of smell score, Lund Mackay CT score and SNOT-22 total score will be analysed in a similar manner to the co-primary endpoints. The pooled analysis of proportion of participants requiring at least 1 course of systemic corticosteroids or disease-modulating medication for CRSwNP or nasal surgery(acutal) will be analysed using a logistic regression model with covariates for treatment group, number of courses of systemic corticosteroids in 12 months prior to screening (0, 1, >1 as ordinal), baseline blood eosinophil count, baseline total endoscopic nasal polyps score, baseline nasal obstruction score (VRS), region, study and previous surgery for nasal polyps. The pooled analysis of ACQ-5 will be based on MMRM with MAR assumption for missing data with covariates for treatment group, baseline score, baseline blood eosinophil count, region, previous surgery for nasal polyps, study, visit and interaction terms for visit by baseline score and visit by treatment group.

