# 1.2. Study Design

### 2. STATISTICAL HYPOTHESES

The study is designed to test the inequality of depemokimab 100 mg SC vs. placebo (both in addition to SoC) in both co-primary endpoints of total endoscopic NP score at Week 52 and mean nasal obstruction VRS symptom score from Week 49 through to Week 52. Each co-primary endpoint will be tested at the two-sided 5% alpha level, both tests are required to be significant to achieve the primary objective of this study.

Demonstration of efficacy for each of these tests will be based on a hypothesis testing approach, whereby the null hypothesis is that there is no difference between treatment groups for the endpoint of interest and the alternative hypothesis is that there is a difference between treatment groups.

[figure not shown]

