#### 4. STATISTICAL ANALYSES

#### 4.1. General Considerations

### 4.1.1. General Methodology

Unless otherwise stated, the Safety Analysis Set be used for safety displays and the Full Analysis Set (FAS) will be used for all other displays. FAS-Modified and Safety-Modified analysis sets will be used for a selected number of displays as sensitivity analyses. FAS-China, FAS-Japan, Safety-China and Safety-Japan will be used for China and Japan specific outputs respectively. The Programming Specification document will provide more details.

Unless otherwise stated, all intercurrent events for primary, secondary, or other endpoints will be handled under the primary estimand strategy.

This SAP specifies the analytical approaches for the global submission requirements, unless otherwise specified. Further analytical considerations may be made for the regional displays (i.e. model convergence considerations) where appropriate.

The randomization is stratified based on occurrence of previous surgery for nasal polyps and unless otherwise stated, this variable will be included as a covariate in the statistical models. In the case of an incorrect stratification at the time of randomization, the actual stratum will be used rather than the randomized stratum.

Confidence intervals will use 95% confidence levels unless otherwise specified.

Unless otherwise specified, continuous data will be summarized using descriptive statistics: n, mean, standard deviation (std), median, minimum and maximum. Categorical data will be summarized as the number and percentage of participants in each category.

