As described in Section 1.1.2, under the primary estimand, the intercurrent events of (i) surgery and (ii) initiation of a disease-modulating medication for CRSwNP, will be handled using a composite strategy by incorporating occurrence of the event into the definition of the endpoint. Specifically, participants who experience the intercurrent event will be assigned the worst possible value of the relevant score for all assessments following the intercurrent event (i.e. the worst value that it is possible to select on the given scale). This means that a participant who experiences the intercurrent event will be assigned a total endoscopic NP score of 8 for every scheduled clinic visit after the date of the first intercurrent intercurrent event (regardless of whether the visit occurred) and a nasal obstruction VRS score of 3 for every day after the date of the first intercurrent event. All other intercurrent events described under the primary estimand strategy in Section 1.1.2 will be handled using a treatment policy strategy.

The study is designed to continue collecting data for participants who have prematurely discontinued from randomized treatment and off-treatment data collected for these participants will be included in the analysis. Missing data will be assumed to be missing at random (MAR). Summary statistics will be produced for each visit/4-week time-period by treatment group for the co-primary endpoints.

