# 5. SAMPLE SIZE DETERMINATION

The sample size for this study is based on the co-primary efficacy endpoints of total endoscopic nasal polyps score at Week 52 and mean nasal obstruction VRS symptoms score from Week 49 through to Week 52, and a pre-specified pooled analysis of data from study 218079 (this study) and study 217095 for the key secondary endpoint of time to first nasal surgery (actual or entry on waiting list).

Approximately 250 participants will be randomised in this study in a ratio of 1:1 giving 125 randomised participants per arm. This sample size allows for up to 5% of randomised participants to be non-evaluable, providing a minimum of 118 evaluable participants per arm in the analyses of primary and secondary endpoints.

For the co-primary efficacy endpoint of total endoscopic nasal polyps score at Week 52, the study has >99% power assuming a true population difference of -1.10 between depending and placebo. This assumes a standard deviation of 1.665 with significance declared at the two-sided 5% significance level. The smallest observed effect which is predicted to result in a statistically significant difference between depending 100 mg SC + SoC and placebo + SoC is a treatment difference of -0.42

For the co-primary efficacy endpoint of mean nasal obstruction VRS score during Weeks 49-52, the study has >99% power assuming a true population difference of -0.70 between depending and placebo. This assumes a standard deviation of 0.84 with significance declared at the two-sided 5% significance level. The smallest observed effect which is predicted to result in a statistically significant difference between depending by 100 mg SC + SoC and placebo + SoC is a treatment difference of -0.21.

The overall power for both co-primary endpoints is >99%.

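### The Lund-Mackay ANCOVA keeps participants with an intercurrent event at the worst score but drops event-free participants with no Week 52 CT, so inclusion depends on the outcome; the bias is small and of uncertain direction

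*SAP*

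**What the plan says.** - **Model.** SAP 4.3.2 separates LMK from the other secondary endpoints. Its analysis "will be performed using an analysis of covariance (ANCOVA) model with covariates of treatment group, baseline score", log baseline eosinophils, region and previous surgery. There is no visit term, because SAP 4.3.1 has a single post-baseline scan, at Week 52.
- **Intercurrent events.** SAP 4.1.1 states that, unless otherwise stated, "all intercurrent events for primary, secondary, or other endpoints will be handled under the primary estimand strategy". Under SAP 1.1.2 and 4.2.1, surgery and the start of a disease-modulating medication take the worst value on the scale at every later assessment. For LMK that is 24.
- **Unattended visits.** SAP 4.2.1 gives the worst value "regardless of whether the visit occurred", but writes this out only for the NP score.
- **Missing data.** The jump-to-reference and tipping-point analyses in SAP 4.2.3 cover only the co-primary endpoints. Protocol 9.3.1 says that "Lund Mackay CT score and SNOT-22 total score will be analysed in a similar manner to the co-primary endpoints", and assumes MAR for those endpoints.
- **Follow-up after withdrawal.** Protocol 7 and 7.1 provide for continued contact about nasal polyp surgery. Protocol 8.2.3 places the second CT at Visit 16 or the early-withdrawal visit.

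**The concern.** Take two participants who withdraw before Week 52, both with a baseline CT and neither with a later scan. One is known to have had surgery and enters the ANCOVA at 24. The other is event-free and is dropped. The chance of being analysed therefore depends on whether the event occurred, and the event fixes the outcome. Event status is not a covariate, so MAR fails for the composite score, and the mean of each arm gives too much weight to events.

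The co-primary MMRM differs in that a withdrawn participant's earlier visits stay in the model; how far that protects it has not been quantified here. The LMK ANCOVA has no earlier CT to draw on, although centrally read NP scores are collected at seven post-baseline visits (Weeks 12, 20, 26, 32, 40, 48 and 52).

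At stake is the estimate, and to a small degree the error rate, of an endpoint tested in the hierarchy, with no planned analysis that would show the effect of the selection.

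**Working it through.** **The plan's own figures.** SAP 5 gives no effect, SD or missing rate for LMK. Its general allowance is that the sample size "allows for up to 5% of randomised participants to be non-evaluable, providing a minimum of 118 evaluable participants per arm": 125 × 0.95 = 118.75, so 118. For the pooled surgery endpoint it gives a placebo event rate of 23% and a hazard ratio of 0.38. The implied drug rate is 1 − 0.77^0.38 = 9.45%. If the replicate study is the same size, pooling gives 236 to 250 per arm and 236 × (0.23 + 0.0945) = 77 to 250 × (0.23 + 0.0945) = 81 events. The critical hazard ratio at two-sided 4.75% is exp(−2 × 1.982/√events) = 0.636 to 0.644, which agrees with the stated 0.64.

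**Inputs for LMK.** Event rates are p = 23% (placebo) and 9.45% (drug). They are upper illustrations, because the planning rate also counts waiting-list entry, which is not an LMK event. Assumed, because the documents give nothing: the event-free Week 52 means μ, and the fraction m of event-free participants without a Week 52 CT. Unscanned event-free participants are taken to resemble scanned ones in the same arm. Unreadable scans are treated as missing; SAP 4.3.1 codes them 9, which is also a possible score on 0–24.

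**Formulas.** Share of worst scores among those analysed: w = p / [p + (1 − p)(1 − m)]. Arm mean: 24w + (1 − w)μ. The target is the same expression with m = 0. The shift in the drug-minus-placebo difference is (w − p)(24 − μ) for drug minus the same term for placebo.

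**Shares.** With m = 5% in both arms, the placebo share is 0.23/(0.23 + 0.77 × 0.95) = 23.9% and the drug share is 0.0945/(0.0945 + 0.9055 × 0.95) = 9.9%.

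**Shift in the difference, in points (negative favours drug):**

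| Event-free means, placebo / drug | Target difference | 5% / 5% loss | 10% / 10% | Placebo 15%, drug 5% | Placebo 5%, drug 15% |
|---|---|---|---|---|---|
| 17 / 17 | −0.95 | −0.03 | −0.07 | −0.18 | +0.04 |
| 18 / 18 | −0.81 | −0.03 | −0.06 | −0.15 | +0.03 |
| 18 / 16 | −2.62 | −0.02 | −0.04 | −0.14 | +0.06 |
| 18 / 12 | −6.25 | 0.00 | 0.00 | −0.13 | +0.12 |
| 20 / 15 | −5.07 | 0.00 | +0.01 | −0.08 | +0.10 |

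**Break-even at equal loss.** The shift is zero when (24 − drug mean)/(24 − placebo mean) equals the placebo (w − p) divided by the drug (w − p). That ratio is 2.05, 2.04 and 2.00 at 5%, 10% and 20% loss. Below about 2 the difference is inflated; above it, attenuated.

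**Simulated ANCOVA** (4,000 trials, 125 per arm, assumed SD). For 18 / 16 the mean estimate moved from −2.58 to −2.60 at 5% loss in both arms, to −2.73 with 15% placebo v 5% drug, and to −2.52 in the mirror case. With no treatment effect and 10% loss in both arms there was no bias (rejection 4.9%). With no effect and 15% v 5%, the bias was 0.13 to 0.14 points towards the arm with less loss, and rejection was 5.5% to 6.1%, against 5.0% to 5.1% with full data.

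**The case against.** A reader might infer that the treatment difference is inflated whenever the drug lowers event rates. The documents do not support that. The mirror case of 15% loss on drug and 5% on placebo attenuated the difference in every scenario run, and nothing in the protocol or SAP says which arm will lose more scans.

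A reader might also express the shift against the event-driven part of the difference alone. In the 17 / 17 row, 0.95 becomes 0.98 (+3.5%), 1.02 (+7%) or 1.13 (+19%), and 0.91 (−4%) in the mirror case. Those percentages assume that the drug has no effect on CT except through events. Against the 18 / 16 total of −2.62, the shift is 0.7% at 5% loss and 5.5% at 15% v 5%.

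Three further points stand:

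- **Not every event participant is kept.** Under SAP 4.1.2 a missing baseline stays missing, so without a baseline CT there is no change score, event or not. Retention without a scan is inferred for LMK.
- **The protocol limits the loss.** After a second dose, the early-withdrawal visit falls at Week 52 and includes the CT. The gap is mainly those who withdraw before the second dose, whose Week 26 scan is discretionary under Protocol 8.2.3, and those who miss the visit. The SAP gives no rule for using a Week 26 scan as the Week 52 value.
- **There is no conflict with the protocol's wording on similar analysis.** With one post-baseline value, the MMRM reduces to this ANCOVA.

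An objection to the remedy also carries weight. Contact after withdrawal is described for surgery and safety, not for the start of disease-modulating medication, so some unscanned participants counted as event-free may have had an event. That calls for a stated assumption and a retained complete-case analysis. It does not remove the selection.

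**Conclusion.** The concern holds as a selection problem with bias of uncertain direction. The difference was inflated in every scenario with more loss on placebo, and at equal loss when the drug arm's event-free distance from 24 is less than about twice that of placebo. It was attenuated above that ratio, and in every scenario run with 15% loss on drug v 5% on placebo.

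Under the assumed means, the size is about 0.02 to 0.03 points at 5% loss in the 18 / 16, 18 / 18 and 17 / 17 cases, and close to zero in the others. At 15% v 5% it is 0.08 to 0.18 points towards inflation if placebo loses more, or 0.03 to 0.12 towards attenuation if drug loses more, on a 0–24 scale. A lower event rate shrinks it: at an assumed 12% on placebo, shifts over 5% to 20% loss ran from about −0.10 to +0.06.

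The effect would rarely change a conclusion. It merits correction because the method does not meet its MAR assumption, no planned analysis would reveal the effect, and the correction is cheap.

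**What to change.** In SAP 4.3.2:

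1. State that participants with surgery or a disease-modulating medication before the Week 52 assessment receive an LMK score of 24 whether or not scanned.
2. Multiply impute missing Week 52 LMK in participants without a recorded event, within arm and under MAR, from event-free participants. Use baseline LMK, the model covariates and the observed NP scores at Weeks 12 to 52 as predictors.
3. Fit the stated ANCOVA to each completed dataset and combine with Rubin's rules.
4. Keep the complete-case ANCOVA as a sensitivity analysis.
5. State the assumption that participants with no recorded event stay event-free after withdrawal, and that starts of disease-modulating medication may not be captured then.

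The cost is SAP wording and modest programming, since multiple imputation with Rubin's rules is already planned for the co-primary endpoints. The downside is the added assumption in step 5. No new data collection is needed.
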